Study Population	Individual who reported aged 18 and above, assigned male sex at birth, ever had anal sex with another man, HIV-negative, identifying as Chinese citizen, currently residing Guangzhou(only applicable in Aim 2), China, and able to and being willing to sign written informed consent and participate in the study as procedures required.
Number of subjects	Total sample size: N=110 Aim 1 (in-depth interviews): n=40 Aim 2 (two-arm RCT): n=70 (intervention arm n=40, control arm n=30)
Number of sites	1
Estimated Start of Enrollment	June 15, 2020
Estimated Time to Completion	June 15, 2021
Protocol Duration	Aim 1: 90 minutes Aim 2: Aim 2: 16 weeks (8-week active intervention and after-intervention follow-up at the 12 th week. Participants in the intervention arm can have access to the intervention app up to 16 weeks.) Participants may choose to participate in either Aim 1 or Aim 2.
Stratification	Participants in Aim 1 will be stratified into three groups: (1) 5 current PrEP users (2) 30 people who have never used PrEP (3) 5 intermittent PrEP users (people who were on PrEP before but now off)
Regimen or Intervention	Aim 1: Formative research/in-depth interviews: no intervention Aim 2: Two-arm RCT: 70 participants will be randomized at enrollment into the intervention arm (n=40) or the standard of care control arm (n=30). All 70 participants will pay an initial visit to the Guangzhou No.8 People's Hospital to complete enrollment and a Web-based baseline assessment survey. 
 • The standard of care control arm: during the initial visit, participants will receive written HIV prevention materials including basic facts of PrEP, recommendations for HIV/STIs testing and referrals to local HIV/STIs testing sites and prevention services. • The intervention arm: In addition to the standard of care, participants in the intervention arm will have access to a mini-app-based PrEP intervention for up to 16 weeks. The mini-app has four main functions: (1) a mini-classroom function that contains a series of HIV-, sexual health-, and PrEP-related educational articles in Chinese; (2) an HIV/Syphilis home-based test kit ordering system that allows users to order a finger-prick HIV rapid test toolkit and shipped to home for free (one piece at a time); (3) an asynchronous

IGHID # 120001

PI: [name]

Version Date: Sept 2, 2020

1.0 OBJECTIVE

1.1 Hypothesis

We hypothesize that in our study sample, adult men who have sex with men (MSM) in the intervention arm are more likely to report successful PrEP initiation at the end of trial, as compared to the control arm.

1.2 Primary Objective

Our primary objectives include:

- (1) Conduct formative research to understand key barriers and facilitators for PrEP uptake among Chinese MSM and test the usability of a mobile-based mini-app intervention.
- (2) Conduct a two-arm pilot randomized control trial to test the efficacy of the mini-app in increasing PrEP uptake rates among Chinese adult MSM.

1.3 Secondary Objectives

Secondary objectives include: in our study sample,

- (1) Test the efficacy of the mini-app in decreasing PrEP stigma and increasing PrEP use self-efficacy at the individual level.
- (2) Identify the predictors associated with successful PrEP initiation during the study period.
- (3) Investigate the association between depression at baseline and successful PrEP initiation during the study period.
- (4) Assess PrEP use adherence among participants who successfully started PrEP during the study period.

2.0 INTRODUCTION

2.1 Background

The prevalence of HIV among Chinese men who have sex with men (MSM) has steadily increased for the past decade. According to the National HIV Sentinel Surveillance System, the prevalence of HIV in Chinese MSM rose from 1.5% in 2005 to 8.0% in 2015.¹ Overall, MSM comprise over a quarter of new HIV diagnoses in China, this greater than three times the rate in other countries.² These trends continue to rise as China works to implement feasible and sustainable HIV prevention measures.

Pre-exposure prophylaxis (PrEP) is a once daily oral fixed-dosed combination of two antiretroviral medications, tenofovir disoproxil fumarate (TDF) and emtricitabine (FTC) also referred to as TDF/FTC. Several clinical trials have demonstrated that PrEP is safe and significantly reduces the rate of HIV acquisition in MSM,³ heterosexual HIV sero-discordant couples,⁴ heterosexual individuals,⁵ and persons who inject drugs.⁶ Based on these studies, in

2014, the United States Centers of Disease Control and Prevention (CDC) issued recommendations for PrEP in MSM, high risk heterosexual men and women, and PWID. These recommendations were updated in 2017 with more trials further supporting PrEP use in these key populations.⁷ In 2014, the World Health Organization (WHO) recommended global access to PrEP for MSM which was then expanded in 2015 to include all populations at substantial risk of HIV infection.⁸

Despite the current HIV landscape of China and the proven safety and efficacy of PrEP, uptake remains limited with only an estimated 400-600 current PrEP users in the country.⁹ The delay in PrEP expansion in China is likely multifactorial, including limited awareness of PrEP, HIV and sexuality-related stigma and discrimination, concerns of PrEP effectiveness and side effects, and financial concerns to afford PrEP.¹⁰⁻¹³ Initial PrEP demonstration projects in China were unsuccessful because of poor community engagement and lack of community ownership.¹¹ Bottom-up approaches such as challenge contests provide a tool for MSM to be more actively engaged in HIV service delivery.¹⁴ A recent multisite survey of urban Chinese MSM showed while nearly half of the respondents endorsed unprotected anal sex, less than a quarter had heard of PrEP.¹⁵ These studies indicate a need in using an MSM-friendly approach to promote PrEP uptake among this at-high-risk population and linking them to PrEP to help stem the ongoing epidemic.

Mobile health (mHealth) intervention tools have become increasingly popular in HIV- and PrEP-related research. Formative studies indicate that mHealth interventions are acceptable and effective in promoting HIV prevention practices in MSM and other young populations.^{16,17} Among the few mHealth-based PrEP intervention studies, text messaging has been effective in improving PrEP adherence in MSM via reducing missed doses¹⁸ and increasing drug concentrations in blood.¹⁹ More mHealth PrEP uptake intervention studies are in the pipeline however all are based in the US.²⁰⁻²³ mHealth shows promise as an intervention tool in places like China where HIV risk factors and infection remains highly stigmatized.²⁴ HIV-related and sexual health interventions delivered through Internet-enabled platforms are feasible and acceptable in Chinese settings,²⁵ including interventions through websites, text message and mobile apps which have shown effectiveness in reducing HIV-related risk behaviors, increasing linkage to care, and medication adherence.²⁶⁻²⁸

2.2 Rationale

While most of our previous knowledge about the acceptability of PrEP in China came from cross-sectional survey studies, little is known from a qualitative perspective about the key concerns and thoughts that Chinese MSM are having of PrEP as an HIV prevention strategy. Further, either globally or in China, limited data exists on the efficacy of app-based interventions aimed to increase PrEP uptake and adherence. Given the gap in knowledge, this proposed study aims to deeply understand the key barriers and facilitators to PrEP uptake among Chinese MSM and their unmet needs in HIV prevention via in-depth interviews, followed by a two-arm pilot randomized controlled trial to test the efficacy of a mini-app in increasing their engagement for PrEP education and initiation. A prototype of the mini-app has been developed from an MSM-friendly

Doctor Finder hackathon contest (April 2019, Guangzhou) by a team of Chinese young MSM. Our study will provide preliminary data for a competitive R01 to fully develop and test this new evidence-based intervention to increase PrEP knowledge and actual uptake in China. If successful, this research will ultimately impact the PrEP/HIV prevention cascade in China by showing that an mHealth intervention can alleviate systemic and psychosocial barriers to HIV prevention services among young Chinese MSM. This research addresses a critical need as MSM bear a disproportionate burden of China's HIV infections and remain underserved in the healthcare system.

3.0 STUDY DESIGN

This study is designed to collect formative data and preliminary efficacy test result of a mini-app that will help inform a future full-scale intervention study to increase PrEP uptake in China. It consists of a formative phase using in-depths interviews (Aim 1, see Figure 1) and an experimental phase using a two-arm randomized controlled trial (RCT) design (Aim 2, see Figure 2).

Aim 1: Understand the key barriers and facilitators of using PrEP, and assess the usability and acceptability of a mobile-based intervention mini-app for PrEP education and initiation among MSM in China via in-depth interviews with 40 HIV-negative young Chinese MSM (18 years old and above) in China.

In Aim 1 we will assess unmet needs in HIV prevention, key barriers and facilitators of PrEP uptake among HIV-negative young MSM in China. We will conduct in-depth interviews with 40 HIV-negative MSM including 30 people who have never used PrEP, 5 people who used PrEP before but are now off treatment, and 5 people who are current PrEP users. All potential participants will be verbally screened for eligibility during their initial contact with the study team. During the interview, participants will be asked to test use a mini-app prototype for 5 minutes on their own smartphone, after a brief instruction on the purpose of the mini-app and how to use it. The mini-app is built in an existing popular social networking app (WeChat) that any user with a test link will be able to access the mini-app via WeChat without downloading additional installments. Then participants will be asked questions about their perceived feasibility and acceptability of the mini-app. A brief demographic survey will be administered at the end of interview. The mini-app has four main functions: (1) a mini-classroom that contains a series of HIV-, sexual health-, and PrEP-related educational articles in Chinese; (2) an HIV/Syphilis duo self-test toolkit ordering system that allows users to order a finger-prick HIV rapid test toolkit and shipped to home for free (one kit per order); (3) an asynchronous message function that allows users to initiate a chat with a study staff; and (4) a user profile page where users can manage all HIV test orders.

Interviewees' demographics and PrEP use history will be recorded in a spreadsheet in order to balance enrollment across all 3 groups (current PrEP users, people who never use PrEP, and intermittent PrEP users). We will use semi-structured interview guides with tailored questions for each group of the participants (see attached in-depth interview guide). In addition to discussing their knowledge, attitudes and willingness to use PrEP and PrEP use history, interviewees will be asked to describe their past pathways to HIV prevention services (e.g., HIV testing, counseling) including struggles and support resources they encountered. After test-using the mini-app, participants will be asked to comment on the design, contents and ease of use of the mini-app. Interviews will be conducted one-on-one in private spaces, last 60-90 minutes and will be audio recorded with participant's permission.

[figure not shown]

Figure 1. Procedure of in-depth interview in Aim 1

Aim 2: Evaluate the preliminary efficacy of the mini-app in changing PrEP perceptions and increasing PrEP uptake among young Chinese MSM (18 years old and above) in Guangzhou, China through a small pilot RCT (n=70), comparing the mini-app (n=40) to the standard of PrEP care (n=30).

Before the start of Aim 2, we will refine the mini-app based on participants' feedback in Aim 1. In Aim 2, we will conduct a pilot two-arm RCT to evaluate the feasibility and acceptability of the mini-app and examine its preliminary efficacy in changing PrEP-related perceptions and increasing actual PrEP initiation compared with a standard of care control group. All potential participants who show interest in participating the study need to complete a verbal eligibility screening during their initial contact with the study team. Those screened eligible and interested in participation will need to make an initial in-person or remote visit at the Guangzhou No.8 People's Hospital, during which they complete a baseline assessment survey after proceeding the full informed consent process. Only participants who express interest in using the mini-app for HIV prevention, meet the eligibility criteria, provide informed consent, and complete a baseline assessment will be assigned a final study ID and be eligible for randomization.

Control: Standard of Care

In the standard of care control arm, participants will receive written HIV prevention materials (hard-copy at the clinic or electronic files) including basic facts of PrEP, recommendations for HIV/STIs testing and referrals to local HIV/STIs testing sites and prevention services.

Intervention: the mini-app

The study intervention tool, a mini-app built within a chat-app (WeChat, available on both Android and iOS systems), serves as the primary participant-facing component of the intervention. The mini-app does not require users to download or install anything as long as they have WeChat installed on their phone. Participants in the intervention arm will be able to access full function of the mini-app for 8 weeks. The mini-app has four main functions: (1) a mini-classroom that contains a series of HIV-, sexual health-, and PrEP-related educational articles in Chinese; (2) an HIV/syphilis home-based test kit ordering system that allows users to order a finger-prick HIV rapid test toolkit and ship to home for free (one toolkit per order allowed; participants can place more than one orders with no upper limit during the intervention period); (3) an asynchronous message function that allows users to communicate with the study team; and (4) a user profile page where users can manage orders of HIV/syphilis test kits. The mini-app is not able to collect or track any individual user information or user activity within the mini-app. It cannot initiate a chat with participants unless the participant requests a chat.

Home-based HIV/Syphilis test kit

The study will use a mail-based system to deliver free HIV/Syphilis test kits to participants upon request. We will use imported Abbott SD BIOLINE HIV/Syphilis Duo test kit that allows users to conduct finger-prick test at home. Participants will receive a plain box via standard mail that includes the test kit with instructions. Participants can also find the instruction of how to use the test kit in the mini-app. Participants do not need to send back any specimen or other material back to the study team, but they will be encouraged to report back test results to the study team via messaging through the mini-app. Testing experience and results will also be asked in the biweekly follow-up surveys.

PrEP initiation

Participants in both arms can choose to initiate PrEP at any time point since the initial visit until the end of 8th week. Participants can contact the study team via phone call, text messages or via the chat function in the mini-app to communicate their interest in PrEP initiation. If baseline assessment or follow-up survey results do not show contradictions to PrEP initiation, interested participants will be referred to the Department of Infectious Diseases at Guangzhou No.8 People's Hospital to consult a clinician regarding HIV risks and PrEP eligibility. As is standard of care for any patient starting PrEP, participants will take comprehensive physical examinations (including routine urine examinations, hepatic and renal function tests, blood glucose and lipids, and bone mineral density (BMD)). The study team will not have access to participants' medical records (i.e. the physical examination results). Participants who are confirmed by the clinician HIV-negative, with no serious liver or kidney dysfunction and negative for HBs antigen, without serology indicating osteoporosis, without clinical signs or symptoms consistent with acute viral

infection, will be prescribed either 8-week daily oral TDF/FTC or event-driven oral TDF/FTC based on participants' preference. The cost of physical examinations in order to get PrEP prescription will be covered by the study team. If a participant is eligible for starting PrEP and have been prescribed PrEP by a PrEP provider, the participant will get a 50% reimbursement of the cost for their first two months of PrEP doses (30 pills/month, up to 60 pills in total) filled at the in-house pharmacy of the study hospital (the Guangzhou Eighth People's Hospital).

Follow-up and Data collection

The active intervention period will last for 8 weeks, but participants in the intervention arm can have access to the mini-app throughout the whole study period or until the end of their first two-month PrEP use, which can be as long as 16 weeks. Baseline assessments will be conducted at the enrollment visit, with follow-up assessments conducted at 2, 4, 6, 8, 12 (post-intervention). Participants from both arms will need to complete a self-administrated Web-based survey at each assessment time point.

In addition to Web-based surveys, a subgroup of participants (n=20) from both the intervention arm and the control arm will receive up to two rounds of in-depth interviews, separately at the 4th and 8th week, to share their experience of using the app and changed perceptions and/or behaviors related to PrEP. Among the 20 participants, 15 will be recruited for interviews during the first and fourth weeks, who will receive two rounds of interviews. Another five participants will be recruited between the 4th and 8th week, who will be only interviewed once at the 8th week. Interview topics include participants' experience of using the app and changed perceptions and/or behaviors related to PrEP and HIV prevention practices during the study period. Interviews will be conducted one-on-one in private spaces, last 60-90 minutes and will be audio recorded with participant's permission.

Referrals

In the case of an initial positive HIV test done through the study, participants who have initiated PrEP will be instructed to discontinue PrEP dosing. Participants testing positive will be referred to the Guangzhou No.8 People's Hospital for confirmation test or other testing places if needed. The Guangzhou Center for Diseases Prevention and Control will be notified of confirmed positive results in accordance with China's public health reporting laws, a procedure that will be explained to participants at consent. For positive syphilis testing results, participants will be referred to STI treatment at the Guangzhou No.8 People's Hospital. The study team will follow-up with participants testing positive for HIV or STIs to encourage participants to seek appropriate care.

[figure not shown]

Figure 2. Flowchart of Aim 2 study design

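### After week 12 nothing scheduled brings a positive home test to the study team, although daily PrEP and app access can run to week 16

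*Combined protocol and SAP*

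**What the plan says.** Section 3.0 (Referrals) sets the action after a first positive study test: "participants who have initiated PrEP will be instructed to discontinue PrEP dosing". The participant is also referred for confirmation, and the team follows up to encourage care.

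Section 3.0 (Home-based HIV/Syphilis test kit) describes how a result becomes known. Nothing is sent back. Participants may volunteer the result: "they will be encouraged to report back test results to the study team via messaging through the mini-app". There is also a scheduled route: "Testing experience and results will also be asked in the biweekly follow-up surveys". Of the app itself, section 3.0 says: "It cannot initiate a chat with participants unless the participant requests a chat".

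Sections 3.0 and 6.1 place the follow-up surveys at weeks 2, 4, 6, 8 and 12. PrEP may be started up to the end of week 8, and those found eligible "will be prescribed either 8-week daily oral TDF/FTC or event-driven oral TDF/FTC". App access lasts through the study period or "until the end of their first two-month PrEP use, which can be as long as 16 weeks".

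The documents differ on kit ordering. Section 3.0 gives full app function for 8 weeks and says that "participants can place more than one orders with no upper limit during the intervention period". The Protocol Summary and section 5.0 describe the app, with its ordering function, as available for up to 16 weeks.

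**The concern.** Stopping PrEP, referring and following up all require the team to know the result. The plan lengthens app access to match a late PrEP course but does not lengthen the schedule of result questions. A man who starts daily PrEP after week 4 is therefore still dosing when the last scheduled question has been asked. If he tests positive at home after that and does not get in touch, the team can follow the plan exactly and never be prompted to act. At stake is the delivery of a safety step that the protocol itself promises, in men enrolled because of recent HIV risk and taking doses that the study partly reimburses.

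**Working it through.** **1. How a home result can reach the team.**
- Specimens: none are collected or handled (section 10.0).
- Clinic records: "The study team will not have access to participants' medical records", with the physical examination results named as the example (section 3.0).
- App: it does not track users and cannot open a chat.
- Interviews: weeks 4 and 8 only, in a subgroup of 20.
- Withdrawal on becoming HIV-positive (section 7.0) and the safety notification in section 8.5 both presuppose that the participant has disclosed the event.

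This leaves contact that he starts himself, and the surveys. Kits are ordered through the app, so the point concerns the intervention arm.

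**2. Reproducing the plan's 16 weeks.** Latest start (end of week 8) + 8-week daily course = week 16, as stated.

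**3. Intervals between scheduled questions.** From enrollment: 2, 2, 2, 2 and 4 weeks, then none. This counts the week 12 survey as asking for results. The plan ties the question to the biweekly surveys, so that reading is inferred and favours the plan.

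**4. Daily dosing after the last question.** A course started at week s ends at week s + 8, so dosing after week 12 = max(0, s − 4).

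| Start week | Course ends | Dosing weeks after week 12 |
|---|---|---|
| 4 or earlier | 12 or earlier | 0 |
| 5 | 13 | 1 |
| 6 | 14 | 2 |
| 7 | 15 | 3 |
| 8 (end) | 16 | 4 |

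**5. Expected size.** The documents give no uptake, start-time, kit-order or incidence figure, so these are assumptions: 10 to 50% of the 40 app-arm men start, all on daily dosing, evenly over weeks 0 to 8; incidence is 1 to 10 per 100 person-years.
- Starters: 0.10 × 40 = 4 to 0.50 × 40 = 20.
- Mean dosing after week 12: half start after week 4, with a mean tail of 2 weeks, so 0.5 × 2 = 1 week per starter.
- Person-weeks: 4 × 1 = 4 to 20 × 1 = 20. Divided by 52.18, this is 0.077 to 0.383 person-years.
- Infections: 0.077 × 0.01 = 0.0008 to 0.383 × 0.10 = 0.038. This is before PrEP protection, and before requiring that a kit is used and the result not reported.

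**6. Sensitivity to start time.** If every start falls by week 4, dosing after week 12 is 0. If every start falls at the end of week 8, it is 4 weeks each: 4 × 4 = 16 to 20 × 4 = 80 person-weeks (0.31 to 1.53 person-years), or 0.003 to 0.15 infections on the same incidence range.

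**7. What added texts would do**, under the even-start assumption.
- Week 14 text, to men still dosing (s > 6, 25%): 1 to 5 texts.
- End-of-course text (s > 4, 50%): 2 to 10 texts. Total: 3 to 15.
- Longest wait after week 12: for starts in weeks 4 to 6 the course ends by week 14; for later starts there is a question at week 14 and another by week 16. The wait is at most 14 days, against no question now.
- Dosing that could be cut short: only dosing after week 14, which is s − 6, at most 2 weeks and on average 1 week among starts after week 6. That is 1 to 5 person-weeks in the whole trial. The end-of-course text cuts none.

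Event-driven users have no stated course length, so their dosing after week 12 cannot be computed.

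**The case against.** The strongest reply is that little is left to fix. The participant reads his own result, can message or call, and received testing referrals at enrollment. The kit and in-app instructions are not reproduced, and they may already tell him to stop PrEP and seek confirmation. If ordering closes at week 8, only leftover kits matter. The expected number of positives is close to zero, and a text at the end of a course comes when there is no dosing left to stop.

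Most of this stands and sets the size of the point. It does not remove it: orders have no upper limit, no use-by rule is stated, and two places in the protocol leave ordering open to week 16. No repeat clinic HIV test after PrEP starts is described.

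A reader might infer that the 28 days between the week 8 and week 12 surveys need an extra prompt as well. The documents do not support that. The week 12 survey covers the interval, if late. A prompt at week 10 would go to one arm just before the week 12 comparison of HIV/STI testing behaviors planned in section 8.6, and could itself change testing. The weekly texts that stop at week 8 only encourage app use, so their ending removes no result question.

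A reader might also infer that the kit instructions omit a stop-PrEP line. Those instructions are not among the documents, so nothing can be concluded about them.

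**Conclusion.** The gap is real but narrow. After week 12 the steps that follow a positive home test have no scheduled trigger, while daily dosing and app access may continue to week 16. On even starts and 10 to 50% uptake of daily PrEP in the app arm, 4 to 20 person-weeks of dosing are involved, or 0.001 to 0.04 infections before PrEP protection. The result depends heavily on when men start, and is zero for daily users if all start by week 4. Any claim about the share of dosing that falls late in the study would rest on an assumed start distribution, for which the documents give no data.

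A reader might go further and infer that men are left without care, or that the trial's results are at risk. Neither follows. The participant knows his result and can seek help, and the primary outcome is fixed at week 8. This is a cheap, optional safety improvement and not a flaw in the design.

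**What to change.** For app-arm men whose first PrEP course or app access runs past week 12, use the existing text-message survey-link channel (section 6.1) to send:

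- one neutral text at week 14, if the man is still dosing;
- one at the end of the course or, for event-driven users, of app access, at week 16 at the latest.

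Each text carries only a link, with no mention of HIV, PrEP or testing. The link opens the existing test-result question, and a positive answer starts the steps in section 3.0 (Referrals). Only the week 14 text can shorten dosing, and only for daily users who started after week 6; the end text serves referral and follow-up. Add no prompt at week 10. It would also help to state when kit ordering closes, since that decides how far the gap extends.

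The cost is about 3 to 15 texts on the assumptions above, and at most 8 to 40 if all 4 to 20 starters received both (2 × 4 to 2 × 20). No new staff or procedure is needed. The downsides are a few extra messages, a small privacy risk if others see the phone, and results that remain self-reported. All texts follow the last outcome survey, so no between-arm comparison is affected.
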